8.5 Quality complaints

In case of quality complaints (technical or transportation claims), the Investigator must report to the Sponsor thereon within 24 hours after receipt of information as described in Appendix 2. Any AE associated with the quality complaints shall be documented and reported as described in Sections 8.3.4 and 8.3.5.

Protocol No. TE_004_ANG_LOZ

Special cases

8.6

Special cases may be serious or non-serious (see below) and must be reported as AEs pursuant to Sections 8.3.4 and 8.3.5 even in absence of other AEs associated with the special cases.

A special case scenario	The Investigator must inform LPPV
Exposure during breastfeeding	X
Intentional overdose by the patient (including the suicide attempts which are always considered to be serious)	
Drug interactions	Only if associated with SAE
Withdrawal response/syndrome	Only if associated with SAE
Drug dependency, misuse, abuse, or addiction (always serious)	X
Suspected transmission of infectious agents (always serious)	X
Death (always serious even without other events)	X

8.7 Information verification

Verification of information between a safety database of the Sponsor and a clinical database stored in CRO will be performed at the end of the trial according to a verification plan by comparison of the relevant summary tables from both databases.

During data processing, eCRF/information in the clinical database will be reviewed for potentially unreported SAEs. Any potential SAE requires an exact match in the following parameters between the clinical database and safety database: trial number, center number, subject number, randomization number, study drug, degree of severity, date of death (if applicable), and causality according to the Investigator's evaluation. All other parameters must be credible and consistent from medical perspective. Thorough verification of information must be performed for every event subject to reporting as well as any other events of special interest (if applicable) considered to be related to the study drug, including dates of the drug use, outcome, medical history, and concomitant therapy.

9 Statistics

9.1 Description of the statistical methods to be used including the terms for every planned interim analysis

Statistical analysis will be performed using R Project specialized software.

The continuous (quantitative) data will be presented as a number of observations, arithmetic mean, confidence interval (CI) 95% for the mean (unless stated otherwise), standard deviation (SD), median, interquartile range (IQR), minimum, and maximum.

The serial, categorical, and qualitative data will be presented as absolute incidences (number of observations), relative incidences (%), and CI 95% (unless otherwise stated).

The concomitant diseases and AEs will be coded using MedDRA terms.

This section contains a brief description of the planned analysis. Full analysis will be presented in the statistical analysis plan.

9.1.1 Demographic and other baseline data (group comparability for the analysis)

All the data obtained in the groups before the trial therapy initiation (demographic, laboratory, instrumental, and physical examinations data, vital signs, etc.) will be compared between the groups to determine the groups' comparability for analysis.

The Fisher's exact test and chi-square will be used to compare the qualitative and serial data, while the t-test or the Mann–Whitney test will be used for the quantitative data (depending on the quantitative data distribution).

9.1.3 Analysis of the secondary efficacy endpoints

- Frequency of ≥50% total score reduction according to the TSS questionnaire completed by the Investigator as compared to the baseline in both Angal S and ANTI-ANGIN® FORMULA groups at Visit 2 (Day 4).
- Total score reduction according to the TSS questionnaire, as well as a reduction in the symptoms (sore throat, difficulty in swallowing, salivation, erythema, and fever) after a 3-day therapy, at Visit 2 (Day 4), as compared to the baseline total score.
- A period of time required for disease symptoms relief, determined according to the patient's diary (subjective patient's evaluation), but no more than 5 days during the trial—for patients who have achieved the corresponding outcome.
- A proportion (%) of patients who fully recovered by Day 4 in Group A and by Day 5 in Group B (the outcome of a disease according to the objective evaluation by the Investigator, the total score according to the TSS questionnaire ≤2).
- A change in the sore throat intensity by 100 mm VAS (visual analogue scale filled in by the patient) at the beginning, after 3 days of therapy, and at the end of treatment in both groups.

The following statistical analysis methods are stipulated for the secondary efficacy endpoints:

• Frequency of ≥50% total score reduction by the TSS questionnaire completed by the Investigator relative to baseline in both Angal S and ANTI-ANGIN® FORMULA arms at Visit 2 (Day 4)—the response frequencies will be compared in each time point using the Fisher's exact test.

- Total score reduction by the TSS questionnaire, as well as reduction in symptoms (sore throat, difficulty in swallowing, salivation, erythema and fever) after 3-day therapy, at Visit 2 (Day 4), relative to baseline total score—the between-arm comparison will be carried out using the Mann–Whitney test due to non-symmetrical nature of the scores distribution in the TSS scale.
- A period of time required for the symptoms resolution defined by the patient's diary (subjective patient's evaluation), but not more than 5 days within the trial (for patients who achieved the relevant outcome)—the between-arm comparison will be carried out using t-test or the Mann–Whitney test depending on the distribution character. The survival will not be evaluated due to low duration of the trial.
- The proportion (%) of patients who fully recovered on Day 4 in Group A and on Day 5 in Group B (disease outcome according to the objective evaluation by the Investigator, the total score by the TSS questionnaire ≤ 2)—the between-arm comparison will be carried out using the Fisher's exact test.
- A change in the sore throat intensity by 100 mm VAS (visual analogue scale filled in by the patient) at the beginning, after 3 days of therapy, and at the end of treatment in both groups—the between-arm comparison will be carried out using the t-test.

A secondary endpoint analysis will be conducted both for the ITT (main analysis) and PP populations (additional analysis).

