4.2.3.2.4 Evaluation of the throat pain intensity according to VAS

The patient will fill in the VAS to evaluate for the throat pain intensity at every visit to the trial site (Visit 1, Visit 2, and Visit 3 (where applicable)). Calibrated scales 100 mm in length with the relevant measuring instruments will be provided for the clinical trial.

The patients should evaluate their pain severity according to VAS at every visit (if possible, before administration of the painkillers (if those are required) or the study drug/comparator drug). The scale is provided in Appendix 5 to this protocol.

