4.2.4 Trial stages

4.2.4.1 Screening/randomization/therapy initiation (Visit 1)

Visit 1 is scheduled for Day 1. At this visit, the doctor evaluates the patient's eligibility for the trial. If no non-inclusion criteria are met, the patient undergoes randomization with further training on the drug use and handling precautions, is given the study drug/comparator drug and a patient's diary, and is instructed on the patient's diary completion requirements.

Screening visit procedures:

- Signing of the Informed Consent Form;
- Demographic data (date of birth, sex, age);
- Measurement of weight and height;
- Anamnesis gathering;
- Records on the concomitant therapy;
- Evaluation of inclusion/non-inclusion criteria;
- Evaluation of the throat pain intensity according to VAS;
- Fill-in of TSS questionnaire by the Investigator;
- Physical examination (including oropharynx);
- Measurement of the main vital signs;
- Hematology;
- Biochemistry;
- Urine pregnancy test;
- 12-lead ECG;
- Evaluation of inclusion/non-inclusion criteria;
- Randomization;
- Training for administration and handling of the study drugs;
- Dispensing of the study drugs;
- Provision with the patient's diaries and training on the fill-in rules;
- Initiation of therapy with the study drugs;
- Evaluation of adverse events (including based on results of the throat and pharynx examination).

Taking into account a dosage form of the study drugs (topical spray), the patients will be instructed on the use and handling the sprinkler, as well as the oral spraying technique. The first dose of the drug will be taken at the trial site under the Investigator's supervision. The patients will be told to turn the tube perpendicularly to the bottle (vial) before the first use. The patient should open his/her mouth wide, direct sprayer towards the pharynx, and press

the sprinkler nozzle. The patient should hold their breath during spraying. After each use, the tube should be turned back down to block the spraying nozzle.

The patients will be also instructed on the sprinkler handling and care rules. In the event that Angal S/ANTI-ANGIN® FORMULA spray will not be used for some time, it is recommended to clean the spray nozzle after the last use according to the following procedure:

- 1. The spray should be turned upside down, and the actuator button should be pressed until the solution remaining in the spraying adapter is removed (solution does not spray out anymore).

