9.3 Applicable significance level

All statistical analyses in this trial will be conducted at 95% significance level (a threshold p value for confirmation of statistical significance is below 0.05), except for the primary endpoint where an onesided statistical criterion will be used with 97.5% significance level (a threshold p value is below 0.025). The two-sided statistical criteria will be used for all other parameters.

For the primary endpoint evaluation, 90% CI will be calculated for the proportions difference with further evaluation of its lower boundary limit.

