9.7 Selection of subjects for analysis

The following data sets will be used for analysis:

• The intention-to-treat (ITT) population: all randomized subjects who received at least one dose of the study drug/placebo and have completed at least one visit aimed at evaluation of the efficacy parameters (i.e., at least all the procedures of Visit 1).

According to the ICH E9 requirements, the ITT population will be considered to be a population for statistical analysis in the equivalence trials (including non-inferiority trials).

- The per protocol (PP) population: all randomized subjects who completed participation in the trial in accordance with the protocol (have completed the prescribed period of treatment and follow-up without significant deviations from the protocol).
- The safety population (safety): All randomized subjects who received at least one dose of the trial/reference drug and have completed at least one visit to the evaluation of the parameters of safety (i.e., at least all the procedures of Visit 1). As distinct from ITT population, the safety population will be analyzed depending on actually received treatment (not only prescribed) (in case of difference between the prescribed and received therapies).

Protocol No. TE_004_ANG_LOZ

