3.8 Acceptable deadlines for visits and a scope of investigations

The data obtained at Visit 1 (Day 1) will be considered to be the initial data for the endpoint analysis.

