4.1.3 Secondary endpoints

The following statistical analysis methods are stipulated for the secondary efficacy endpoints:

- The frequency of ≥50% total score reduction by the TSS questionnaire completed by the Investigator relative to baseline in both Angal S and ANTI-ANGIN® FORMULA arms at Visit 2 (Day 4)—the response frequencies will be compared in each time point using the Fisher's exact test.
- Total score reduction by the TSS questionnaire, as well as reduction in symptoms (sore throat, difficulty in swallowing, salivation, erythema and fever) after 3-day therapy, at Visit 2 (Day 4), relative to baseline total score—the between-arm comparison will be carried out using the Mann—Whitney test due to non-symmetrical nature of the scores distribution in the TSS scale.
- A period of time required for the symptoms resolution defined by the patient's diary (subjective patient's evaluation), but not more than 5 days within the trial (for patients who achieved the relevant outcome)—the between-arm comparison will be carried out using t-test or the Mann–Whitney test depending on the distribution character. The survival will not be evaluated due to low duration of the trial.
- The proportion (%) of patients who fully recovered on Day 4 in Group A and on Day 5 in Group B (disease outcome according to the objective evaluation by the Investigator, the total score by the TSS questionnaire ≤ 2)—the between-arm comparison will be carried out using the Fisher's exact test.
- A change in the sore throat intensity by 100 mm VAS (visual analogue scale filled in by the patient) at the beginning, after 3 days of therapy, and at the end of treatment in both groups—the between-arm comparison will be carried out using the t-test.

A secondary endpoint analysis will be conducted both for the ITT (main analysis) and PP populations (additional analysis).

A multifactorial analysis of the secondary endpoints is not envisaged.

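### VAS sore-throat pain is compared by an unadjusted t-test although baseline VAS is collected before randomization; ANCOVA would be at least as precise, by an amount the documents cannot fix

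*Protocol*

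**What the plan says.** The endpoint wording begins "A change in the sore throat intensity by 100 mm VAS (visual analogue scale filled in by the patient) at the beginning, after 3 days"; a third assessment, when therapy stops, completes the list. In Protocol 9.1.3 the method is one clause: "the between-arm comparison will be carried out using the t-test". SAP 4.1.3 repeats it and closes the list of secondary analyses with "A multifactorial analysis of the secondary endpoints is not envisaged". No efficacy endpoint has a baseline covariate in either document. ANOVA appears only for safety and laboratory values (Protocol 9.1.4, SAP 4.1.5).

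The covariate is already planned:

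- Protocol 4.2.4.1 lists "Evaluation of the throat pain intensity according to VAS" among the Visit 1 procedures, ahead of randomization.
- Protocol 4.2.3.2.4 says "The patient will fill in the VAS to evaluate for the throat pain intensity at every visit to the trial site".
- SAP 3.8 fixes the baseline: "The data obtained at Visit 1 (Day 1) will be considered to be the initial data for the endpoint analysis".
- Protocol 9.7 defines ITT membership as completing "at least all the procedures of Visit 1", so every ITT patient should have a baseline VAS.

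Outside the primary endpoint, tests are two-sided with "a threshold p value for confirmation of statistical significance is below 0.05" (Protocol 9.3). SAP section 4 confines the non-inferiority conclusion to the primary parameter and treats secondary variables as of research interest.

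**The concern.** A t-test on change from baseline fixes the coefficient of baseline VAS at 1, and a t-test on the Day 4 value fixes it at 0. ANCOVA estimates it. Unless the fixed value happens to be right, the t-test carries variance that could be removed. It also leaves chance baseline imbalance in the estimate: through regression to the mean for change, and directly for Day 4 values. Protocol 9.1.1 compares baseline data between arms, but the plan does not say what follows if VAS differs.

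At stake is the precision of the one continuous pain score that patients give themselves. A further gap is that neither document plans a between-arm VAS difference with a confidence interval; the 95% CI in SAP section 4 is for each mean. In a non-inferiority trial a non-significant t-test does not show similarity, whereas an adjusted difference with its interval can be read directly.

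**Working it through.** **No plan figure to reproduce.** The documents state no VAS SD, correlation, target difference or power. The correlations below are assumptions.

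**Formulas.** Let s0 and s1 be the baseline and Day 4 SDs, k = s1/s0, and r their correlation. The large-sample variances per patient are:

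- change score: s0² + s1² − 2·r·s0·s1
- Day 4 value: s1²
- ANCOVA: s1²·(1 − r²)

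The change-score variance minus the ANCOVA variance is (s0 − r·s1)². This is never negative, and it is zero only when the slope of Day 4 on baseline, r·k, equals 1. The Day 4 variance minus the ANCOVA variance is r²·s1², which is zero only at r = 0.

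**Against the change score.** The ratio of ANCOVA to change-score variance is k²(1 − r²)/(1 + k² − 2rk).

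*Equal SDs (k = 1).* The ratio reduces to (1 + r)/2.

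- r = 0.2: 0.60, saving 40%, worth 1/0.60 − 1 = 67% more patients
- r = 0.4: 0.70, saving 30%, worth 43% more
- r = 0.6: 0.80, saving 20%, worth 25% more

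A simulation with 128 per arm and 3,000 runs gave 0.64, 0.76 and 0.84 at r = 0.3, 0.5 and 0.7, against 0.65, 0.75 and 0.85 by formula.

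*Day 4 SD larger than baseline.* The only relevant spread in the documents is the four-level sore-throat item in the placebo-controlled lozenge trial (Protocol 9.2, Table 2). Scoring the product arm 0 to 3:

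- Baseline, counts 0/3/77/26 (n = 106): mean 235/106 = 2.217, SD 0.478
- Day 4, counts 65/27/11/1 (n = 104): mean 52/104 = 0.500, SD 0.724
- k = 0.724/0.478 = 1.51 (placebo arm 1.58)

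With k = 1.514 (k² = 2.293):

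- r = 0.2: 2.201/2.687 = 0.819, saving 18%
- r = 0.4: 1.926/2.081 = 0.925, saving 7%
- r = 0.6: 1.467/1.476 = 0.994, saving about 1%

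*Day 4 SD smaller than baseline.* With k = 0.75 the ratio is 0.46 to 0.56 for r = 0.3 to 0.7, so the gain could also exceed the equal-SD range.

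**Against a t-test on Day 4 values.** The ratio is 1 − r²: 0.96, 0.84 and 0.64 at r = 0.2, 0.4 and 0.6. The savings are 4%, 16% and 36%. They rise with r, whereas the equal-SD saving against change falls with r.

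**Cost in precision.** One degree of freedom multiplies the variance by about 1 + 1/(2n − 4). With n = 128 per arm this is 1 + 1/252 = 1.004.

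**Time point.** Protocol Table 1 and 4.2.3.2.4 place VAS at Visit 2 in both arms. Visit 3 (Day 5) exists only for Group B patients not recovered at Visit 2, so end-of-treatment VAS falls on Day 4 in Group A and on Day 4 or 5 in Group B.

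**The case against.** The strongest reply is that this is an efficiency preference on an unpowered endpoint, with a gain that may be close to nothing. Under randomization the t-test is unbiased. VAS is the last of five secondary endpoints. On the only spread the documents offer, the saving against the change score falls to about 1% at a correlation of 0.6, which nearly cancels against the 0.4% cost of the extra parameter. This stands as a limit on size. The proxy is a four-level item from a lozenge trial, not VAS, so it shows that a large gain cannot be assumed; it does not show that the gain is small.

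It is also unclear that change is what will be tested. SAP Table 17 summarises VAS by visit with a p row and has no change column. That ambiguity is real, but ANCOVA is at least as precise under either reading, and naming one model would resolve it.

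A reader might infer four stronger things that the documents do not support:

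- *That adjustment is worth 25–67% more patients.* That needs equal SDs, which nothing in the documents establishes.
- *That the change score loses whenever the correlation is below 1.* The condition is a slope different from 1. At k = 1.5 and r of about 0.67 the two methods tie.
- *That VAS is the main support for an investigator-rated primary endpoint in an open trial.* No passage gives it that role. The patient diary (Appendix 3) tells patients that they know their drug, so VAS is exposed to the same open-label bias, which ANCOVA does not touch.
- *That the change is a costless SAP edit.* The method also stands in the Protocol. Protocol 11.2 classes amendments that may influence statistical methods as significant, and SAP section 1 says the SAP makes no changes from the Protocol.

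**Conclusion.** The point holds as a modest improvement. The plan discards a baseline measurement that it already collects before randomization, and the SAP confirms that no adjustment is intended. The direction is certain in large samples: ANCOVA is never less precise, beats the change score unless the slope is 1, and beats the Day 4 value unless the correlation is 0.

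The size is not known. The ranges in the brief rest on assumed correlations of 0.2 to 0.6 and on the stated SD ratios, and neither VAS quantity is in the documents. The t-test is valid as it stands. The non-inferiority conclusion and the planned sample size do not depend on this choice.

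**What to change.** In Protocol 9.1.3 and SAP 4.1.3:

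- Analyse VAS at Visit 2 (Day 4) by ANCOVA with arm and baseline (Visit 1) VAS as terms.
- Report the adjusted mean difference with a two-sided 95% CI.
- Reword the SAP sentence that excludes multifactorial analysis so that it permits this model, and add the adjusted difference to SAP Table 17.
- Keep end-of-treatment VAS descriptive, because its timing differs by arm and adjustment does not cure that.

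If the Protocol is not to be amended, Protocol 9.6 allows a deviation to be described and justified in the final report, provided that an SAP written before the final analysis lists it with reasons.

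The cost is one degree of freedom (about 0.4% of variance at 128 per arm), plus the approvals for an amendment or the justification for a deviation. No new data are needed.

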9.1.4 Safety parameters analysis

A descriptive part of the safety analysis will include an evaluation of incidences and two-sided CI 95% for the following parameters in every trial group:

- AEs: the incidence in total and for separate categories (according to MedDRA), for the trial and by groups;
- SAEs: the incidence in total and for separate categories (according to MedDRA), for the trial and by groups;
- Incidence of clinically significant changes of the physical examination results by visits and groups;
- Incidence of clinically significant changes of the laboratory results by visits and groups;
- Incidence of clinically significant changes of the vital signs (body temperature, BP, pulse rate, HR) by visits and groups;
- Incidence of clinically significant changes of the ECG parameters by visits and groups;
- Global tolerance evaluation during the trial by the Investigator and patient.

The Fisher's exact test will be used to compare incidences between the groups, and chi-square will be used to compare the global therapy tolerability by the Investigator and patient. The McNemar's test will be used to evaluate for the dynamic changes during the trial (before—after) for all the repeatedly evaluated incidences in every group.

In addition to the incidence, all the quantitative safety parameters will be presented in a table form (laboratory results, vital signs, ECG) by visits and groups. The difference will be evaluated using 2-way-ANOVA (group and visit numbers will serve as the relevant factors). The post-hoc criteria will be used in case of significant difference.

Safety analysis will be performed on the safety population.

